10.2 Incidence of Disease-Related Complications

All disease-related complications are collected through day 90 and will be listed.

The number and percentage of subjects with at least one occurrence of each of the following disease-related complications after Day 1 will be presented by treatment and by visit, Anticipated disease progression includes, but not limited to:

- HE – including HE I, HE II, HE III, and HE IV
- Gastrointestinal (GI) Bleeding – including lower GI bleeding and upper GI bleeding
- Portal Hypertension
- Ascites
- Spontaneous Bacterial Peritonitis (SBP)
- Hepatorenal syndrome (HRS) – including Type 1 and Type 2
- Associated organ/system failure(s) – to be defined and summarized as described in [9.3.8](#)

In addition, the number of each type of disease-related complication will be counted for each subject and presented by treatment as a continuous variable and as a categorical variable with categories 0, 1, 2, 3, 4 or more. No analysis of treatment differences will be performed. Each type of HE, Gastrointestinal (GI) Bleeding, Hepatorenal syndrome(HRS) and associated organ/system failures will be counted separately.

10.3 Clinical Laboratory Evaluations

Clinical laboratory samples will be analyzed by a central laboratory; the table below lists the planned tests for each panel. All lab tests including unplanned ones will be included in the laboratory listings and summaries.

Test Panel	Planned tests
Hematology	Hemoglobin, hematocrit, platelets, red blood cell count, white blood cell count with differential
Chemistry	Sodium, potassium, creatinine, blood urea nitrogen (BUN), calcium, magnesium, lactate dehydrogenase (LDH), aspartate aminotransferase (AST), alanine aminotransferase (ALT), gamma-glutamyl transpeptidase (GGT), alkaline phosphatase (ALP), glucose, total bilirubin, direct and indirect bilirubin, C-reactive protein (CRP), lactate, serum albumin
Coagulation	International normalized ratio (INR), fibrinogen, platelet count, prothrombin time
Systemic inflammation assessment	Procalcitonin, WBC (hematology panel), CRP (chemistry panel)
Biomarker retains	Blood biomarker Post-PE-A 5% plasma biomarker obtained from plasma removed during the first 15 minutes and the last 15 minutes of the PE-A 5% session

Laboratory parameters will be presented in alphabetical order within test panel; the differential of WBC counts will be presented alphabetically following the WBC results.

All results and normal ranges will be displayed in SI units. All data will be listed for each subject. Values outside of normal range will be flagged.

Systemic inflammation assessment summaries are described in section [9.3.6](#).

For all other continuous/quantitative laboratory parameters (hematology, chemistry, coagulation), summary tables will present descriptive statistics for original values and change in value from baseline by parameter, treatment, and scheduled visit. For SMT+PE-A 5% group, change from baseline to the pre-exchange timepoint will be summarized. Moreover, the difference in value between pre-exchange and post-exchange within each visit will also be summarized. Assessments after Liver transplant will be removed from summaries and analysis but will be provided in the listing.

For summarization, concentration values that are reported as "<X.XX" the concentration will be imputed using the X.XX value multiplied by a factor of 0.9. For concentration values that are reported as ">X.XX" the concentration will be imputed by using the X.XX value multiplied by a factor of 1.1.

For example:

Standard lab result =<0.2 then analysis result=0.2*0.9

Standard lab result =>0.2 then analysis result=0.2*1.1

Shifts from baseline (with categories L/N/H for low/normal/high) will be presented by parameter, scheduled visit, and treatment.

Instituto Grifols, S.A. / Protocol IG1407

Laboratory results that are outside of the normal range will be evaluated by the investigator, and if determined to be clinically significant, will be reported as an adverse event. Clinical significance will not be reported in the laboratory listings or summaries.

Biomarker retains will be drawn for potential analysis of cytokines (interleukin [IL] 6 (IL-6), IL-8, IL-10, and tumor necrosis factor alpha [TNF α]) and other candidate biomarkers found in the blood which may correlate with disease activity. These samples will be frozen and stored for possible future use and will not be included in this analysis. All biomarker sample results obtained will be provided in a listing.

10.4 Vital Signs

Vital signs for systolic and diastolic blood pressure (mmHg), heart rate (bpm), temperature (°C), and respiration rate (breaths/min) will be listed for each subject.

For each vital sign parameter, absolute values and changes from baseline will be summarized descriptively by visit for SMT group. For SMT+PE-A 5% group, change from baseline to the pre-exchange timepoint will be summarized. Moreover, the difference between pre-exchange and post-exchange within each visit will also be summarized.

Assessments after Liver transplant will be removed from summaries and analysis.

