8.2.2 Vital Signs

Vital signs will be measured by a medically certified individual or a nurse according to his/her standard clinical practice.

The following vital signs will be assessed:

- Temperature
- Blood pressure (systolic and diastolic BP)
- Heart rate
- Respiratory rate

Vital signs will be routinely monitored by the study staff as detailed in [Appendix 1](#) and [Appendix 2](#). The investigator will be required to classify vital signs abnormalities as clinically significant or not according to his/her criteria. Results will be recorded in source documents and on the subject’s eCRF. Vital signs abnormalities judged by the investigator as clinically significant will be considered AEs.

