8.3.1 Warnings/Precautions

For complete information on Albutein 5% refer to the IB.

Plasma Exchange is a safe technique that may induce very well-known and therefore preventable and controllable AEs, according to the guidelines provided below. Considering the special vulnerability of the subjects studied, a number of precautions (in addition to the habitual measures) will be taken to minimize the risks of the procedure:

- PE will be carried out by specialized certified personnel, under direct and continuous supervision by the specialized physicians (intensivists, hepatologists, and hematologists).
- Vital signs and laboratory test parameters will be monitored more frequently than usual.

There are AEs that may be expected during the replacement procedure, due to the process of apheresis, the replacement fluid used, or as a result of the subject disease or idiosyncrasy. These AEs include, but not limited to, hypocalcaemia (manifesting as paresthesias, headache, vision alterations, nausea, cramps and chest oppression), anaemia and coagulation disorders secondary to coagulation factor dilution (mainly hypofibrinogenemia, with possible minor bleeding associated to severe thrombocytopenia), hypotension (accompanied by paleness, perspiration, bradycardia, nausea, vomiting, syncope, sphincter relaxation and seizures) (though the risk is minimal, since the infusion amount is equivalent to the extracted amount), allergic reactions with urticaria, dyspnea, wheezing, hypotension, tachycardia, facial reddening and palpebral edema, and AEs related to vascular access. Other events may be of psychological origin or may be inherent to the process, such as anxiety, headache, nausea, immunoglobulin level decreased, anemia, or pain after remaining immobile for several hours. However, these AEs will still be required to be reported.

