9.1.3.3 Vital Signs

Vital signs (T, RR, HR, SBP, and DBP) will be listed for each subject and summarized by treatment group. In case a subject presents a clinically significant abnormality of vital signs during a PE session, the event will be flagged and reported as an AE temporally associated with the PE session.

Clinically significant vital signs abnormalities will be presented as AEs. Clinical relevance will be based on the investigator’s criteria.

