7.3 Demographics

Demographics (age, sex, race, and ethnicity), baseline weight, and stratification factors for randomization will be listed and summarized. Subjects who were incorrectly stratified at the time of randomization will be listed and summarized.

Baseline characteristics listed above will be compared to evaluate possible imbalance by using Student's t test for continuous variables, Chi-square test for binomial or nominal variables, and Poisson model for count variables (with adjustment for overdispersion). All demographic and baseline characteristics data will be listed. Summaries will be provided by treatment group for ITT population.

In addition, the following baseline characteristics will be summarized; ACLF grade, Ascites Grade, Ascites Refractory occurrences, Ascites Refractory Type, CLIF-C ACLF score, CLIF-C OF total score, Child-Pugh Score, MELD Score, country.

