9.3.12 Serum Albumin Concentration

Serum albumin concentration is measured at each visit through the Day 90 visit and is measured before and after each PE-A 5% session at each visit during the treatment period.

Albumin level in serum will be listed for each subject and summarized by each scheduled visit for the SMT group. A summary table will present descriptive statistics for original values and change in value from baseline. For SMT+PE-A 5% group, change from baseline to the pre-exchange timepoint will be summarized. Moreover, the difference between pre-exchange and post-exchange within each visit will also be summarized.

Assessments after Liver transplant will be removed from summaries and analysis.

Instituto Grifols, S.A. / Protocol IG1407

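### Read literally, SAP 10.4 tabulates absolute vital signs for the SMT group only, which is narrower than the both-arm summary in protocol 9.1.3.3

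*SAP*

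**What the plan says.** SAP 10.4 first provides for a listing of blood pressure, heart rate, temperature and respiration rate for each subject. Three summary statements follow:

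- The one statement that mentions levels reads: "absolute values and changes from baseline will be summarized descriptively by visit for SMT group".
- Next comes the first of two items about the plasma-exchange arm: "For SMT+PE-A 5% group, change from baseline to the pre-exchange timepoint will be summarized".
- The second item about that arm concerns the readings around each session: "Moreover, the difference between pre-exchange and post-exchange within each visit will also be summarized".

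Only the first concerns levels, and it names only the control arm.

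Protocol 9.1.3.3 covers the same data more broadly: the five vital signs are to be listed for each subject and summarised by treatment group. It adds that if a clinically significant abnormality occurs during a session, "the event will be flagged and reported as an AE temporally associated with the PE session". Protocol 9.1.3 says that safety comparisons between the arms rest on review of descriptive statistics.

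**The concern.** Plasma exchange can itself disturb haemodynamics. Protocol 8.3.1 lists hypotension among the events that may be expected during the procedure, although it calls the risk minimal because the infused volume matches the volume removed. SAP 5.4.2 makes vital signs a safety variable, with emphasis on readings before and after each session. The plan therefore collects paired readings in the exposed arm, but its wording sends only their differences to the tables.

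A programmer who followed SAP 10.4 to the letter would produce a table of absolute values for SMT alone. Levels could then not be compared between arms in the summaries, and a reader could not see from them where pressures stood before or after an exchange. That would fall short of protocol 9.1.3.3.

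**Working it through.** The plan states no figure on this point, so the check is mainly a comparison of texts.

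**Step 1. What each text covers.**

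| Source | Absolute values, SMT | Absolute values, PE arm | Differences, PE arm |
|---|---|---|---|
| Protocol 9.1.3.3, vital signs | summarised by group | summarised by group | not specified |
| SAP 10.4, vital signs | yes, by visit | not named | baseline to pre-exchange; pre to post |
| SAP 10.3, laboratory | yes, by treatment and visit | yes, by treatment and visit | baseline to pre-exchange; pre to post |
| SAP 9.3.12, serum albumin | yes | covered by a general sentence | baseline to pre-exchange; pre to post |

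SAP 10.3 and 10.4 use nearly the same two sentences for the PE arm. In 10.3 they follow a clause covering both arms; in 10.4 they follow a clause restricted to SMT. SAP 9.3.12 also mentions the SMT group, but then adds "A summary table will present descriptive statistics for original values and change in value from baseline", with no restriction by arm. SAP 10.4 has no such sentence.

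**Step 2. Can PE-arm levels be rebuilt from other tables?** A mean level could be approximated by adding mean change to mean baseline, but baseline vital signs are not tabulated either. SAP 7.3 says: "Demographics (age, sex, race, and ethnicity), baseline weight, and stratification factors for randomization will be listed and summarized". Its further list of baseline items (ACLF grade, ascites, severity scores, country) contains no vital sign.

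**Step 3. Is the narrowing declared?** SAP section 12 lists changes to longitudinal outcomes, ascites, subgroups, the transplant sensitivity analysis and adverse-event categories. It does not mention vital signs.

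**Step 4. Do difference summaries stand in for levels?** A constructed example shows that they need not; it is not a prediction. Take 100 sessions, 50 with pre-exchange systolic pressure 130 mmHg and 50 with 105.

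- Pattern A: the 130 sessions fall by 15 and the others are unchanged. Post-exchange values are 50 at 115 and 50 at 105.
- Pattern B: the 105 sessions fall by 15 and the others are unchanged. Post-exchange values are 50 at 130 and 50 at 90.

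In both patterns the pre/post difference has mean (50 × −15 + 50 × 0)/100 = −7.5, SD 7.5 × √(100/99) = 7.54, and range −15 to 0. Pre-exchange values are the same in A and B, so the change from baseline to pre-exchange is also the same for any given baselines. The two summaries planned for the PE arm would print identically.

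Absolute post-exchange values separate the patterns:

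- A: mean (115 + 105)/2 = 110, SD 5 × √(100/99) = 5.03, minimum 105.
- B: mean (130 + 90)/2 = 110, SD 20 × √(100/99) = 20.10, minimum 90.

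**Step 5. How many readings are involved?** As designed, about 190 subjects with 4 to 9 sessions each give 190 × 4 = 760 to 190 × 9 = 1,710 paired readings. The actual number will be lower because the study stopped early (SAP section 2).

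**The case against.** The strongest reply is that nothing is lost and the wording is merely loose. Much of this stands.

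- The values are not hidden. SAP 10.4 lists them by subject, and SAP 6.1.5 puts all visits in the listings. A reader might infer that the report would contain no PE-arm pressures, but only the summary is missing.
- Procedural hypotension has its own route. Protocol 8.3.1 says of the expected procedural events, "However, these AEs will still be required to be reported". Protocol 8.2.2 adds: "Vital signs abnormalities judged by the investigator as clinically significant will be considered AEs". SAP 10.1 tabulates temporally associated events and gives a rate per session by preferred term, and SAP 8.3 counts exchanges interrupted because of adverse events. A reader might infer that low pressure linked to an exchange would go uncounted. That holds for SAP 10.4 alone, not for the SAP as a whole. The adverse-event route also reaches low points during a session, which pre and post readings miss.
- The circulatory sub-score (SAP 9.3.2 and Appendix 4) shows mean arterial pressure below 70 mmHg and vasopressor use by treatment and visit.
- The laboratory wording, the protocol commitment and the silence of SAP section 12 all point to a slip. The documents do not support the inference that PE-arm levels were left out on purpose.

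Some of the point survives. The adverse-event counts depend on an investigator in an open-label study judging a value clinically significant, and their window runs to 72 hours after a session. The sub-score has no stated timing relative to the exchange. Listings leave the reader to do the summarising. A slip that a programmer can follow literally still needs correcting.

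**Conclusion.** Wrong as written, minor. On its literal wording SAP 10.4 omits absolute vital-sign summaries for the SMT+PE-A 5% arm. This is narrower than protocol 9.1.3.3, out of line with SAP 10.3, and not declared in SAP section 12.

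The size is one missing set of rows in a descriptive safety table. The primary endpoint, alpha and power are unaffected. The conclusion rests on reading SAP 10.4 literally; if the tables are in fact programmed for both arms, only the text needs correcting. The numerical example uses invented inputs and shows only that differences do not determine levels. It says nothing about how often pressure was low in this trial.

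It would go too far to say that the plan must count sessions ending below a set pressure. Neither document calls for such a count. The 70 mmHg cut-off comes from the organ-failure score and is not a protocol definition of procedural hypotension.

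**What to change.** In SAP 10.4:

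1. Change the first summary sentence so that absolute values and changes from baseline are given by visit and treatment group, not for SMT alone.
2. For the PE arm, tabulate absolute pre-exchange and absolute post-exchange values of systolic and diastolic pressure, heart rate, respiratory rate and temperature beside the two planned differences.
3. State that the pre-exchange and post-exchange records are chosen separately under the selection rules in SAP 6.1.5 and the vital-sign footnotes in Appendix 5, so that the rule for multiple readings in one window does not drop one of the pair.

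The readings are already collected, and Appendix 5 already assigns pre and post by the date and time of the exchange. The cost is a few more rows in a descriptive table. A count of sessions ending below a stated pressure is optional. If it is added, the threshold should be labelled as a descriptive choice, and the adverse-event tables should remain the source for low pressure during a session.

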10.5 Physical Assessment

Physical assessment findings (normal and abnormal) will be listed for each subject and summarized by treatment and visit. Any clinically significant abnormality, as determined by the investigator, experienced by a subject during the clinical study and not already present at baseline will be reported as an AE.

11 Interim Analysis

No interim analysis is planned.

12 Changes in Planned Analysis

Changes in the analysis of longitudinal outcomes

The MMRM will be used to analyze the longitudinal continuous outcomes [e.g., CLIF-C OF score, CLIF-C ACLF score, MELD score, Child-Pugh score and Systemic inflammation assessment], and a general linear model implemented in SAS Proc GENMOD will be used to analyze the longitudinal binary or ordinal outcomes [Child-Pugh Sub-Score, CLIF-C OF Sub-Score]. However, protocol section 9.1.2.4 stated that exploratory endpoints would be analyzed by means of analysis of covariance (ANCOVA); this method is not suitable for longitudinal outcomes with missing data.

Adding Ascites Assessment as an exploratory endpoint

Although not included as an exploratory objective in the protocol an Ascites assessment is performed at each visit. The Ascites assessments will be summarized by visit and presented as an exploratory efficacy endpoint. This has been added for completeness.

Exploratory Endpoints

The protocol states the analyses of the primary and secondary efficacy endpoints and exploratory time to event endpoints will be repeated for each sub-group of subjects with ACLF-1b, ACLF-2, or ACLF-3a for exploratory purposes. *Additional subgroup analyses by age group, sex, race, and region (EU versus NA) may be performed for the primary endpoint.* Region was pre-specified as the only additional sub-group analysis on the primary endpoint and this sub-group analyses will also be performed on the secondary and exploratory time-to-event endpoints. This additional by region sub-group analyses is performed to determine if there are treatment effect differences in regions.

Adding a sensitivity analysis in which liver transplant is not a censoring event for the endpoints

A sensitivity analysis will be added to not consider liver transplant as a censoring event in time to death endpoints. This analysis is incorporated in the appropriate sections above (see section [9.1.3](#), [9.2.3](#))

Adding additional categories in treatment emergent adverse event (TEAE)

Appendix 1 – Schedule of Study Procedures and Events

Procedures and Evaluation	Study Period Study Day	Screening	Treatment Period ^a																
		-10 to -1	1	2	3	4	5	6	7	8	9	10	11	12	13	14	15	16	17
Inclusion/exclusion criteria		X																	
Medical history & demographics		X																	
Chest X-ray		X																	
ECG		X																	
Abdominal ultrasound		X																	
Urine pregnancy test		X																	
Physical exam ^b		X																	
Randomization			X																
Vital signs ^c		X	X	X	X	X	X	X	X	X	X	X	X	X	X	X	X	X	X
Ascites assessment		X	X	X	X	X	X	X	X	X	X	X	X	X	X	X	X	X	X
Weight		X	X	X	X	X	X	X	X	X	X	X	X	X	X	X	X	X	X
HE assessment ^e		X	X	X	X	X	X	X	X	X	X	X	X	X	X	X	X	X	X
Hemodynamics assessment ^f		X	X	X	X	X	X	X	X	X	X	X	X	X	X	X	X	X	X
Peripheral oxygen saturation (SpO ₂) assessment		X	X	X	X	X	X	X	X	X	X	X	X	X	X	X	X	X	X
Clinical laboratory assessments ^g		X	X	X	X	X	X	X	X	X	X	X	X	X	X	X	X	X	X
Infection surveillance ^h		X			X		X		X		X		X		X		X		X
Microbiology tests ⁱ		X																	
Record ACLF grade ^{ki}		X	X	X	X	X	X	X	X	X	X	X	X	X	X	X	X	X	X
Illness severity scores ^k		X	X	X	X	X	X	X	X	X	X	X	X	X	X	X	X	X	X
Systemic inflammation assessment ^{lk}			X	X		X		X		X		X		X		X		X	
Blood biomarker retains ^m		X			X				X										X
Post-PE-A 5% biomarker retains ⁿ			X	X		X		X		X		X		X		X		X	
PE-A 5% (1.2 plasma vol) ^o			X	X		X		X		X		X		X		X		X	
IVIG infusion ^p					X				X		X		X		X		X		X
Prior and concomitant medications ^p		X ⁿ	X	X	X	X	X	X	X	X	X	X	X	X	X	X	X	X	X
Adverse events		X	X	X	X	X	X	X	X	X	X	X	X	X	X	X	X	X	X

^a Depending on clinical response, subjects may not complete all treatment days. For subjects in the SMT+PE-A 5% treatment group, PE-A 5% treatment may stop early depending on clinical response. For all subjects, if a subject receives a liver transplant, study treatment will be discontinued. All subjects who remain in the hospital will continue to have Treatment Period assessments performed up through Hospital Discharge. Follow-up assessments for Days 21, 28, 60, and 90 will be performed for all subject

^b Full physical examination (excluding breast and genitourinary examination).

Instituto Grifols, S.A. / Protocol IG1407

-
- ^c Vital signs include systolic blood pressure, diastolic blood pressure, heart rate, body temperature, and respiratory rate. For subjects in the SMT+PE-A 5% treatment group, vital signs will be measured immediately before and immediately after each PE-A 5% session.
 - ^d HE assessment as per Protocol Appendix 9.
 - ^e Hemodynamics (MAP) will be monitored.
 - ^f Clinical laboratory assessments will include hematology, chemistry, and coagulation. For subjects in the SMT+PE-A 5% treatment group, assessment will be performed immediately before and immediately after each PE-A 5% session. For subjects in the SMT group, clinical laboratory assessments will be performed on Days 1 and 2, followed by every other day.
 - ^g Infection surveillance if positive result obtained at Screening Visit using microbiology (cultures) including blood, urine, ascetic fluid, sputum, and pleural fluid. If a positive result occurs at screening, a Day 3 result will be collected. If a thoracentesis or paracentesis has been performed within the last 5 days prior to screening, results of the fluid cultures should be documented in the medical notes. Microbiology cultures will be performed at local labs and the results will be captured in the subject's source documents but will not be entered into the eCRF. All new infections will be recorded as AEs and recorded in subject's source documents and the eCRF. Additional samples will be obtained upon clinical suspicion.
 - ^h Microbiology testing includes cytomegalovirus, polymerase chain reaction, and galactomannan antigen index.
 - ⁱ ACLF grade ([Table 8-1](#)).
 - ^j Illness severity scores include CLIF-C OF score, CLIF-C ACLF score, Child-Pugh score, and MELD score criteria
 - ^k Systemic inflammation assessment includes testing for procalcitonin, WBC (part of hematology panel), and CRP (part of chemistry panel).
 - ^l For subjects in the SMT+PE-A 5% treatment group, blood biomarker retain samples will be collected prior to IVIG infusion (Screening, Days 3, 7, and 17).
 - ^m Applies to subjects in the SMT+PE-A 5% treatment group only. Post-PE-A 5% plasma biomarker retains will be collected after each PE-A 5% session from the plasma bag on Days 1, 2, 4, 6, 8 10, 12, 14, 16.
 - ⁿ Applies to subjects in the SMT+PE-A 5% treatment group only.
 - ^o IVIG 200 mg/kg will be administered every 2 PE sessions on Day 3, 7, 11, or 15. IVIG 100 mg/kg will be administered 1 day after the last, odd-numbered PE session on Days 9, 13, or 17.
 - ^p Record prior (30 days prior to screening) and concomitant medications.

Instituto Grifols, S.A. / Protocol IG1407

